# Investigator Studies Program (MISP) Protocol Template

## Requirements for Submitting a Full Proposal

### Section #1 - MISP Protocol Identification

Study Title:	The title of the protocol should include study design, indication and, where applicable, dosage, dosage form, and comparative agent(s).  A randomized prospective study to compare the effectiveness of Neostigmine versus Sugammadex in length of PACU stay in ASA II and III patients undergoing sleeve gastrectomy bariatric surgery
Request Date:	May 1
Institution Name	Virtua Memorial Hospital
Investigator Contact Information: – Full address – Phone No. – Fax No. – e-mail address	[name] [name] [contact] [contact]

Section #2- Core Protocol	
2.1 Objectives & Hypotheses	
2.1 List the objectives.
 
Objective 1: Determine the difference in length of PACU stay from PACU arrival until ready for PACU discharge for ASA II and III patients reversed with Sugammadex versus Neostigmine in sleeve gastrectomy surgeries.
 
Objective 2: Assess the incidence of PONV in ASA II and III patients reversed with Sugammadex versus Neostigmine, with the prediction that there will be a lower incidence of PONV in the Sugammadex group.
 
Objective 3: Assess the incidence of respiratory complications postoperatively specifically looking at oxygen saturation at 10 minutes after patient arrival to PACU and 60 minutes after arrival to PACU and any intervention necessary.
 
2.1.1 List the clinical hypotheses.
 
The main hypothesis is that Sugammadex given to reverse non-depolarizing muscle relaxants will expedite patients having bariatric surgery out of the PACU
 
Bariatric patients receiving Sugammadex will have less PONV due to the fact that an adverse effect of Neostigmine is nausea and/or vomiting.
 
Patients' status post sleeve gastrectomy surgeries who receive sugammadex will have less respiratory complications than their counterparts who receive neostigmine and thus show a higher PACU oxygen saturation since sugammadex binds and reverses the non-depolarizer muscle relaxants more effectively.

t2.2 Background & Rationale, Significance of Selected Topic & Preliminary Data	
Sugammadex has been demonstrated to shorten the time to reach a train-of-four ratio of 0.9 as well as the extubation time, resulting in improvement of operating room turnover in clinical anesthesia settings, including neuromuscular monitoring.
 
Sugammadex may be recommended for the reversal of neuromuscular block in surgery that requires deep blockade to facilitate surgical procedures. From this point of view, bariatric surgery meets the indications for sugammadex use. Therefore, we frequently use this agent for the reversal of neuromuscular block in sleeve gastrectomy's, duodenal switches, and gastric bypasses.
 
We aimed to investigate whether sugammadex shortens recovery time in the PACU. Currently the average length of stay for our sleeve gastrectomy's performed by one of our bariatric surgeons, [name], is 112 minutes over the last 17 months for ASA II and III patients. A secondary endpoint we want to measure is the incidence in postoperative nausea and vomiting with Sugammadex as compared to neostigmine. We hypothesize that sugammadex will shorten PACU recovery time, and that it will reduce PONV in patients undergoing sleeve gastrectomy bariatric surgeries.
 
Morbid obese population is increasing every year worldwide, and laparoscopic bariatric surgery has a central role in their treatment. The postoperative period of these patients is not free from complications. The introduction of sugammadex has brought huge developments in patient's safety and now laparoscopic sleeve gastrectomy surgery is performed with better care and quality

	
The rationale for conducting this study is to show that Sugammadex is more effective than Neostigmine in reversing non-depolarizing muscle relaxants. This will be demonstrated by the shorter ready for PACU discharge time leading to less cost. It will also show that there will be less post-operative respiratory complications in the Sugammadex group, including but not limited to PONV.
 
A study by Park ES in the BMC Anesthesiology showed that sugammadex can shorten anesthesia and extubation times as well as recovery time in the PACU and reduce postoperative hemodynamic complications in a clinical setting in the absence of neuromuscular monitoring. This may enhance the patients' recovery in the OR and PACU while improving the postoperative condition of patients (1). Sugammadex has been demonstrated to decrease the incidence of post-operative respiratory complications and related costs in patients with OSA. After extubation, desaturation which is defined as <math>\text{SpO}_2 <90\%</math> was observed in 32.4% of the neostigmine group and in 10.8% in the sugammadex group (2). It was also shown that patient receiving sugammadex over neostigmine had a shorter PACU stay (2). A comparison of sugammadex and neostigmine in children for reversal of rocuronium-induced neuromuscular blockade in children demonstrated a faster recovery and extubation times and lower incidence of adverse events compared with neostigmine (5).
 
Sugammadex has been associated with less PONV and a faster discharge from the PACU in laparoscopic bariatric surgeries. In the first hour postoperatively, 27% of patients in the neostigmine group had PONV versus only 8% in the sugammadex group were observed to have nausea and/or vomiting (3). A retrospective investigation of postoperative outcome after reversal of residual neuromuscular blockade in the Eur J Anaesthesiol showed that neuromuscular blockade reversal with sugammadex was associated with lowest rate of PONV and may reduce the risk of pulmonary complications in elderly ASA 3/4 patients (4).

2.3 Study Design	
The study is a randomized, interventional, controlled, blinded, single center study. There will be a minimum of 126 study patients, with 63 patients in the neostigmine group and 63 patients in the Sugammadex group.
 
Inclusion criteria:
 
 
• Patients having sleeve gastrectomy
 
• Surgeries performed by [name]
 
• BMI <math>>35</math>
 
• ASA II and III patients
 
• +/- hiatal hernia repairs with the sleeve gastrectomy
 
 
Exclusion criteria:
 
 
• Patients having a different type of bariatric surgery including but not limited to duodenal switch, gastric bypass, hand-assisted laparoscopic sleeve gastrectomy
 
• Sleeve gastrectomy's performed by other surgeons than [name].
 
• Pregnancy
 
• Allergic to sugammadex, Zofran or scopolamine
 
• COPD or Asthma that is uncontrolled
 
• ASA I, IV, V patients
 
 
Primary parameter:
 
 
• Assess the difference in length of PACU stay from PACU arrival until medically ready for PACU discharge and also from time of administration of reversal agent (which will be start of skin closure) until medically ready for PACU discharge
 
 
Secondary parameter:
 
 
• Assess the incidence of PONV in patients by asking the patients every 15 minutes after arrival to PACU if they are having nausea or vomiting
 
 
Exploratory parameter:

	
 
Assess the incidence of respiratory complications postoperatively looking at oxygen saturation every 15 minutes after PACU arrival and any intervention necessary
 

2.4 Study Flowchart	
The bariatric surgeon, [name], has already agreed to have their patients in the study. The next step is to get IRB approval. The patients will be consented prior to surgery and their signed consents would be kept in our study records. We will track these patients after the surgery in the PACU until discharge and assess their length of stay and possible nausea / vomiting. The exact time we are looking for is patient arrival to PACU until patient ready for discharge when the anesthesiologist writes the anesthesia evaluation. We will also take into account the time the reversal agent is administered during the start of skin closure until patient medically ready to leave the PACU. Blinded to the treatment group, an individual will ask each patient every 15 minutes after arrival to PACU if they are experiencing nausea or vomiting. As an exploratory measure, we will assess the patient at these same times (every 15 minutes) and determine their oxygen saturation. Then we will take all the results and use statistical means to measure what is significant. A discussion and conclusion will follow. Finally I will submit this to an anesthesia journal.

2.5 Study Procedures	
The initial screening period will identify the patients that fit in the inclusion criteria and get their consent to be in the study. There will be two measurements of length of time to assess. One measurement will be from the time the reversal agent is administered which will be the start of skin closure to the patient ready for discharge from the PACU. The second duration of treatment will be the patients' stay in the PACU from arrival from the operating room until ready for discharge based on anesthesia evaluation completed. The criteria for readiness for discharge are based on a modified Aldrete Score >8. The assessor will be blinded to the study group. Readiness will be assessed every 5 minutes. The control group will be the patients who receive the Neostigmine in a dose of 5mg, along with the anti-cholinergic Glycopyrrolate 0.6mg. Sugammadex will be given in a dose of 2mg/kg if the train of four twitch count is 2 and 4mg/kg if the twitch response has reached 1-2 post-tetanic counts with no twitch response to train of four. Monitoring neuromuscular response will be with the device SunStim Plus by SunMed. The end point when we will give the reversal agent is a T1 or T2 block of the adductor pollicis muscle on the twitch monitor. Our standard criteria for extubation include full reversal of muscle relaxation with sustained tetany and a TOF ratio of > .9. We also require adequate oxygenation SpO2>92%, adequate ventilation with tidal volumes >5 ml/kg, spontaneous RR >7bpm, and the patient to be hemodynamically stable. All patients in both the control and study group will receive a Scopolamine 1.5mg patch instructed to place behind the ear the night prior to coming in for surgery and Ondansetron 4mg given 30 minutes prior to the end of the surgery. All patients will be induced with the standard medications of Lidocaine, Fentanyl, Propofol and Rocuronium unless clinically indicated. The patients will be standardized to receive the volatile anesthetic Sevoflurane. Nitrous Oxide will not be given to any patient since this can increase the likelihood of PONV. From a pain management standpoint, fentanyl and hydromorphone will be administered intraoperatively based on the patient's requirements at the discretion of the anesthesia team. The standard inflation pressure at our institution is 18mmHg. The surgeon makes a judicious effort to remove CO2 at the end of the surgery as well to help this cause because residual CO2 can lead a patient to have nausea. The individual who assesses the PONV in the PACU will do so at q 15 minute intervals when VS are checked. They will be blinded to neostigmine and sugammadex treatment. If the patient has PONV, the RN will administer Ondansetron 4mg. If the patient still has PONV then they will administer 25 mg of Diphenhydramine and a third option would be Promethazine 12.5 mg.


2.6 Study Duration	
At our institution [name] currently averages about 13 ASA II and III sleeve gastrectomy bariatric surgeries a month. We therefore anticipate that it will take approximately 10 months for patient recruitment and study completion.

	
Both a statistician and I will be responsible for analyzing the study data. The PONV data will be blinded, with the individual(s) responsible for asking the patient if they're experiencing nausea not made aware of which reversal agent was given.
 
Variables/Time Points of Interest
 
The assessment of PONV:
 
 
• A blinded individual will ask patients at 15 minute intervals in the PACU after arrival to the recovery room until ready for discharge
 
• It will be a check box with yes and no being the only outcome.
 
• If the patient has PONV at any point in the PACU it is considered positive for PONV.
 
 
The assessment of time spent in the PACU:
 
 
• Defined as the time from arrival in PACU to ready for PACU discharge (Anesthesia Evaluation completed). The other time measurement is from administration of the reversal agent during the start of skin closure to the patient being ready for PACU discharge.
 
 
Cost Analysis
 
 
• Knowing the cost per 30 minute increment after the first hour stay in the PACU Phase 1 is \$59.32, the prediction of a 15 minute decrease in PACU stay will equate to a cost savings of approximately \$30/patient in time spent in the PACU
 

2.7 Statistical Analysis and Sample Size Justification	
Statistical Methods
 
The primary outcome measure is the difference in mean PACU Phase 1 LOS minutes between the two groups for which the two sample t-test will be utilized. While the historical (January 2016 to May 2017) PACU Phase 1 LOS (minutes) data did not appear to follow a normal distribution (P-Value = 0.005), they were however found to be lognormally distributed (P-Value = 0.123) [see appendix]. The t-test will therefore be conducted using the log-transformed data. A two sample t-test on the log-transformed PACU data showed that there was no significant difference in geometric mean PACU LOS between ASA II (101.19 minutes) and III (109.62 minutes) patients (P-Value = 0.131). We therefore find it reasonable to include ASA II and III patients in the study.
 
The secondary analysis will use the z-test for proportions since we are looking at the percentages of PONV "yes" outcomes. The exploratory parameter analysis will use the z-test for proportions since we are looking at the percentages of post op respiratory "yes" outcomes.
 
Power/Sample Size:
 
Based on an 80% power to detect a 15% difference in PACU LOS minutes between the two groups and a standard deviation of 0.2634 for the log-transformed data, a minimum sample size of 57 patients per group is needed. Applying a 10% markup against the derived minimum sample size, we will enroll a minimum of 63 patients in each group for a total of 126 study patients.
 
A documented study in the literature (3) revealed that in the first hour postoperatively, 27% of patients in the neostigmine group had PONV versus 8% in the sugammadex group. According to another study (2), after extubation, desaturation (spO2<90%) was observed in 32.4% of the neostigmine group versus 10.8% in the sugammadex group. With 63 patients in each study group, statistical

	powers of 80.9% and 84.7% are estimated for the PONV test and respiratory complications test respectively.
2.8 Specific Drug Supply Requirements	For US and non-US studies, the investigator will be responsible for the destruction of the supplies at the study center pursuant to the ICH/GCP Guidelines, local regulations and the investigator's institutional policies. Clinical supplies must be received by a designated person at the study site, handled and stored safely and properly, and kept in a secured location to which only the investigator and designated assistants have access. Clinical supplies are dispensed in accordance with the protocol. The investigator is responsible for keeping accurate records of the clinical supplies, the amount dispensed to and returned by the patients, and the disposition at the end of the study.
2.9 Adverse Experience Reporting	The study agreement outlines the requirement for adverse experience reporting. For clinical protocols, specific adverse experience reporting requirements must be identified in the protocol if the Model Study Agreement is not used (in general, this would apply to non-US studies whose local requirements may prohibit the use of the agreement).
2.10 Itemized Study Budget	Please refer to the Budget spreadsheet for specifics.

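### PONV is defined over the whole PACU stay but captured only by asking about current symptoms every 15 minutes, so an episode between checks can go unrecorded

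*Combined protocol and SAP*

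**What the plan says.** The endpoint rule is in section 2.6, under Variables/Time Points of Interest: "If the patient has PONV at any point in the PACU it is considered positive for PONV". That is an incidence over the whole stay.

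The measurement is described in four places, each time as a question about the present moment or with no recall period:

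- Section 2.3, secondary parameter: "asking the patients every 15 minutes after arrival to PACU if they are having nausea or vomiting".
- Section 2.4: "an individual will ask each patient every 15 minutes after arrival to PACU if they are experiencing nausea or vomiting".
- Section 2.5: a blinded individual assesses PONV every 15 minutes, when vital signs are taken.
- Section 2.6: a blinded individual asks at 15-minute intervals until the patient is ready for discharge. On the form, "It will be a check box with yes and no being the only outcome".

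On rescue, section 2.5 says "If the patient has PONV, the RN will administer Ondansetron 4mg", with two further agents if symptoms continue. No section links rescue use, or vomiting seen by the nurse, to the endpoint.

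Section 2.7 bases the PONV power on a cited study of the first postoperative hour, in which "27% of patients in the neostigmine group had PONV versus 8% in the sugammadex group". With 63 per group, "powers of 80.9% and 84.7% are estimated for the PONV test and respiratory complications test respectively".

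**The concern.** The definition and the instrument measure different things. A patient who is nauseated at minute 20 and well by minute 30 can truthfully deny symptoms at minutes 15 and 30. The section 2.6 rule makes that patient positive, yet nothing in the described procedure collects the information. Two people completing the box could then score the same patient differently, one from the answers and one from the chart.

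The last part of the stay is exposed too. Section 2.5 has readiness assessed every 5 minutes, so a patient can be declared ready between two PONV checks, and no closing question is described.

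PONV is the only secondary parameter and a stated hypothesis. If episodes are missed in the same proportion in both arms, both recorded rates fall, the absolute difference shrinks with them, and power is lost. Answers that were never asked for cannot be recovered afterwards.

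**Working it through.** **Inputs.** From section 2.7: p1 = 0.27 (neostigmine), p2 = 0.08 (sugammadex), n = 63 per group, z-test for proportions, stated power 80.9%. Alpha and sidedness are not stated; two-sided 5% is assumed. The share of PONV patients missed, m, is not in the documents and is varied.

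**Step 1: reproduce the plan's figure.** For the pooled-variance z-test,

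power = Φ( [ (p1 − p2) − 1.96·SE0 ] / SE1 ), with SE0 = √(2·p̄(1 − p̄)/n), SE1 = √([p1(1 − p1) + p2(1 − p2)]/n) and p̄ = (p1 + p2)/2.

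- p̄ = 0.175; SE0 = √(2 × 0.175 × 0.825 / 63) = 0.0677
- SE1 = √((0.1971 + 0.0736) / 63) = 0.0656
- (0.19 − 1.96 × 0.0677) / 0.0656 = 0.874, and Φ(0.874) = 80.9%

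This matches section 2.7 and supports the assumed two-sided 5%.

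**Step 2: the same share missed in both arms.** Each rate is multiplied by (1 − m), taking 27% and 8% as complete. The ratio of the rates is unchanged, but the difference shrinks.

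| Missed | Recorded rates | Difference (points) | Power, n = 63 | n per group for 80% |
|---|---|---|---|---|
| 0% | 27.0% vs 8.0% | 19.0 | 80.9% | 62 |
| 2% | 26.5% vs 7.8% | 18.6 | 79.9% | 64 |
| 5% | 25.7% vs 7.6% | 18.1 | 78.4% | 66 |
| 10% | 24.3% vs 7.2% | 17.1 | 75.6% | 71 |
| 20% | 21.6% vs 6.4% | 15.2 | 69.5% | 81 |

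The 10% row in full: p̄ = 0.1575, SE0 = 0.0649, SE1 = 0.0631, (0.171 − 1.96 × 0.0649) / 0.0631 = 0.694, Φ = 75.6%.

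**Step 3: what such a miss share would require.** A single episode of L minutes (L below 15), starting at random between checks, is caught with probability L/15. If 20% of PONV patients had one 10-minute episode and all others were caught, m = 0.20 × (1 − 10/15) = 6.7% and power is 77.5%. If 10% did, m = 3.3% and power is 79.2%. Large losses need most patients to have one short episode: if all had a single 10-minute episode, m = 33% and power is 60.2%. Persistent or repeated symptoms lose less, because one positive check is enough.

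**Step 4: effects in other directions.**

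- Missing 10% in the neostigmine arm only (24.3% vs 8%) gives 70.5%. Missing 10% in the sugammadex arm only (27% vs 7.2%) gives 84.8%.
- The benchmark covers one hour, while section 2.6 observes until readiness for discharge; section 2.2 gives an average historical stay of 112 minutes. If the longer window raised both rates by 25% (an assumption), 20% missed would be cancelled exactly, since 1.25 × 0.80 = 1.00, and power would return to 80.9%.

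**The case against.** The strongest case on the other side has five parts.

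1. The section 2.6 rule is explicit, and the present tense elsewhere may be shorthand rather than the wording of the question. This stands in part. A reader might infer that between-check episodes are scored as no; the documents nowhere say so, and the rule says the reverse. What is missing is a route by which such an episode reaches the form.
2. In section 2.5 rescue is described straight after the 15-minute assessment, so it may follow a positive check, and treated patients would already be yes. That reading is open; the text neither confirms it nor confines rescue to the checks. The further agents for continuing symptoms also suggest that many episodes would last to a later check.
3. The cited 27% and 8% are observed rates, and the documents do not describe how that study collected them. If it also used periodic questions, discounting them counts the same loss twice. This stands, and is why step 2 is conditional.
4. The longer observation window and unequal misses can offset or reverse the loss. This stands.
5. Letting rescue use define the endpoint has its own risk: section 2.5 blinds the PONV assessor but does not state that the nurse giving rescue is blinded. This stands and limits the fix.

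None of these closes the gap between a whole-stay definition and a question about the present moment.

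**Conclusion.** The point holds as a mismatch between definition and measurement. The described ascertainment does not guarantee the endpoint in section 2.6, because an episode confined to the interval between checks, or after the last one, can go unrecorded.

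A reader might go further and infer that the trial does not have its stated power. The documents do not support that. The 80.9% is correct for its inputs, and neither episode length nor miss rate is given. The figure is not assured, and its margin is thin: 2% missed equally takes it just under 80%. The illustrative range is 78.4% to 69.5% for 5% to 20% missed. It rests on equal misses in both arms, complete benchmark rates, 63 analysed per group and a two-sided 5% test. Outside those assumptions power could be lower or higher.

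This concerns a secondary endpoint and does not affect the primary comparison. It is worth correcting because the better question is nearly free.

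**What to change.** In sections 2.3, 2.4, 2.5 and 2.6, have the blinded assessor ask at each 15-minute check, and once more at the end of the PACU observation period, about any nausea or vomiting since the previous check (since PACU arrival at the first). Score PONV yes if any answer is yes.

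Vomiting or a rescue antiemetic given for PONV, as shown in the existing PACU record, may also count as yes if those recording or giving it are blinded to the reversal agent; the plan should state whether they are. If they are not, keep the assessor-based endpoint as the main analysis and report the version with record data as a sensitivity analysis.

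The cost is a reworded question, one closing question and, if used, a look at records already kept. Assessor and check times stay the same. The downside is slight reliance on recall over at most 15 minutes. The change should be made before data collection. No change to rescue treatment is proposed.

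### Section 2.2 expects the trial to show less cost, but the only cost analysis prices PACU minutes and omits the reversal drugs, so no conclusion about net cost can be drawn from it

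*Combined protocol and SAP*

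**What the plan says.** Section 2.2 (Background & Rationale) gives the reason for the trial as showing that sugammadex reverses the block more effectively, and adds: "This will be demonstrated by the shorter ready for PACU discharge time leading to less cost". The word cost carries no qualifier there.

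The only method for cost is one item headed Cost Analysis, placed after Section 2.6 (Study Duration). It starts from a unit cost, "Knowing the cost per 30 minute increment after the first hour stay in the PACU Phase 1 is" $59.32, and continues that "the prediction of a 15 minute decrease in PACU stay will equate to a cost savings of approximately" $30 per patient "in time spent in the PACU".

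Section 2.5 (Study Procedures) sets out the drugs being compared. The control arm receives "Neostigmine in a dose of 5mg, along with the anti-cholinergic Glycopyrrolate 0.6mg", a fixed amount. In the other arm, "Sugammadex will be given in a dose of 2mg/kg if the train of four twitch count is 2 and 4mg/kg" at a deeper level of block, so the amount depends on body weight and depth of block. Section 2.3 restricts entry to patients with BMI above 35.

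No section gives a price for any of the three drugs, or says that their cost will be collected or set against the PACU saving. Cost is absent from the objectives and hypotheses (2.1), from the primary, secondary and exploratory parameters (2.3) and from the statistical methods (2.7). Section 2.10 points to a budget spreadsheet that is not among the documents; it is cited as the study budget, not as an analysis.

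**The concern.** The reversal agent is the randomised intervention, so its cost is the one cost that differs between the arms by design. The cost method leaves it out and keeps only a downstream consequence, PACU time. Followed as written, a shorter sugammadex stay is reported as less cost whatever the drugs cost.

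At stake is the economic statement in the rationale, which could be carried into the publication planned in Section 2.12. A reader of that report would take less cost to mean that using sugammadex costs the hospital less. The planned calculation could not show this, even if the stay shortened exactly as predicted.

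**Working it through.** **Inputs from the documents**
- PACU unit cost: $59.32 per 30 minutes after the first hour (Cost Analysis, after 2.6).
- Predicted reduction in stay: 15 minutes (same place).
- Historical mean stay: 112 minutes (2.2). SD of log stay: 0.2634 (2.7). Group size: 63 (2.3, 2.7).

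**Input not in the documents**
- D = mean reversal-drug cost per patient in the sugammadex arm minus that in the neostigmine plus glycopyrrolate arm. D is treated as unknown, and the values used below are assumptions.

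**Step 1. Reproduce the stated figure.** Rate per minute = 59.32/30 = $1.977. Saving = 59.32 x 15/30 = $29.66, which rounds to the stated $30. The figure has one term, minutes saved.

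**Step 2. Add the missing term.** Net saving = $29.66 - D. Break-even is at D = $29.66. For a given D, the reduction in stay needed to break even is D/1.977 minutes.

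| Assumed D | Net saving per patient | Reduction in stay needed to break even |
|---|---|---|
| $0 | +$29.66 | 0 min |
| $10 | +$19.66 | 5.1 min |
| $29.66 | $0.00 | 15.0 min |
| $50 | -$20.34 | 25.3 min |
| $100 | -$70.34 | 50.6 min |

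The table shows how the result moves with D. It does not suggest which row applies.

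**Step 3. Precision of the PACU part alone.** The rate is quoted per 30-minute increment. Suppose whole increments are charged (an assumption), stay is lognormal with mean 112 minutes and log SD 0.2634, and every patient's stay is shortened by 15 minutes. Simulation then gives a mean saving of about $29.60 and an SD of cost per patient of about $61.7. The standard error of the difference is 61.7 x sqrt(2/63) = $11.0, and the 95% half-width is 1.96 x 11.0 = about $21.6. About half of patients would save nothing and the rest one full increment. A predicted saving near $30 would thus carry an interval of roughly $8 to $51 (29.60 - 21.6 and 29.60 + 21.6) before drug cost and its variability enter. No interval is planned.

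**The case against.** The strongest reply is that the plan has already scoped the figure. The Cost Analysis item confines the $30 to PACU time, Section 2.2 ties cost to readiness time in the same sentence, and nowhere is sugammadex said to be cheaper overall. Cost is not an endpoint, and the item is worded as a prediction, so a full cost comparison would add something the trial never set out to do.

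Much of this stands. The $30 is correct for what it describes, PACU-time cost can be compared between arms, and the consequence is limited to the economic conclusion. What does not stand is that this scoping reaches Section 2.2, where less cost is unqualified and is presented as something the trial will demonstrate. Either the claim or the analysis has to move.

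A reader might also infer four stronger points that the documents do not support:
- *That the direction of the cost result is settled in advance.* It is not. A longer sugammadex stay would appear as a higher cost, and no difference in stay as no saving. Only a shorter stay is bound to appear as a saving.
- *That sugammadex costs more overall.* No price is given, so neither the size nor the sign of D is known.
- *That the costing uses the wrong end time because PACU charges run until the patient leaves.* The documents do not say when charging stops.
- *That the supply records in Section 2.8 already provide the drug-cost data.* That section says "The investigator is responsible for keeping accurate records of the clinical supplies, the amount dispensed to and returned by the patients". This covers quantities, not prices, and does not say whether neostigmine and glycopyrrolate count as clinical supplies.

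**Conclusion.** The point holds as a mismatch between claim and method. The stated saving of about $30 is arithmetically sound for PACU time ($29.66), but it cannot support an unqualified statement of less cost because the reversal drugs are left out. The predicted saving vanishes once the sugammadex arm's reversal-drug cost exceeds the control arm's by more than $29.66 per patient.

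The break-even rests on the plan's own unit cost, its 15-minute prediction and pro-rata costing of time beyond the first hour. The half-width of about $21.6 rests further on the lognormal and whole-increment assumptions, and serves only to show that an interval is needed. The plan should be changed on this point, but the primary comparison of PACU stay and the sample size of 63 per group do not depend on it.

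**What to change.** Preferred: in the Cost Analysis item after Section 2.6, define cost per patient as PACU-time cost plus reversal-drug cost, in both arms. Drug cost is the amount of each reversal agent used multiplied by a unit price from a named institutional source. State whether PACU time is costed pro rata or in whole 30-minute increments. Report the difference between arms in mean total cost with a bootstrap 95% confidence interval, with the PACU-time and drug components shown separately.

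Alternative: if drug cost will not be collected, change Section 2.2 to claim less PACU-time cost, and keep any later report within that limit.

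The preferred change costs a price lookup, recording of the amounts used and one extra calculation; the alternative changes a few words. The downside for the sponsor is that the stated saving may become less favourable.

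### Does quoting PONV and respiratory power at 63 per group, when the primary was sized at 57, overstate those powers?

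*Combined protocol and SAP*

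**What the plan says.** Section 2.7 (Power/Sample Size) takes three steps.

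- **Primary.** The calculation is "Based on an 80% power to detect a 15% difference in PACU LOS minutes between the two groups", with "a standard deviation of 0.2634 for the log-transformed data", and concludes that "a minimum sample size of 57 patients per group is needed".
- **Enrolment.** "Applying a 10% markup against the derived minimum sample size, we will enroll a minimum of 63 patients in each group". No reason is given for the 10%.
- **Other endpoints.** The sentence opens "With 63 patients in each study group" and goes on to say that "powers of 80.9% and 84.7% are estimated for the PONV test and respiratory complications test respectively". The rates come from two cited studies: 27% versus 8% for PONV and 32.4% versus 10.8% for desaturation.

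Section 2.3 gives the same enrolment: "There will be a minimum of 126 study patients, with 63 patients in the neostigmine group and 63 patients in the Sugammadex group". It classes PONV as secondary and respiratory complications as exploratory. For the test, section 2.7 says "The secondary analysis will use the z-test for proportions", and it names the same test for the exploratory parameter. It states neither alpha nor sidedness.

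**The concern.** A markup of this kind is often an allowance for patients who cannot be analysed. Read that way, 57 is the number expected in the analysis and 63 the number recruited to secure it. The primary's 80% would then be a power after losses, while the PONV and respiratory powers would assume no losses.

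PONV is where this would show. Its stated power is only 0.9 points above 80%, and by the plan's formula 62 per group are needed to reach 80%. Someone who sets the primary's 80% beside PONV's 80.9% might think the two equally well powered, although at equal numbers PONV is about three points lower. If the PONV comparison were then non-significant, the chance of missing a real effect would have been understated. PONV is the only secondary endpoint and one of the stated clinical hypotheses, so the question deserves a check.

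**Working it through.** **Inputs.** From section 2.7: PONV 0.27 versus 0.08; desaturation 0.324 versus 0.108; log-scale SD 0.2634; 15% difference; 57 and 63 per group. Alpha is assumed to be two-sided 0.05. This assumption reproduces 57, 80.9% and 84.7%; one-sided 0.05 at 63 per group would give 88.5% and 91.1%.

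**Primary.** Effect size = ln(1.15)/0.2634 = 0.1398/0.2634 = 0.531. The two-sample t-test then needs 56.7, so 57 per group, which matches the plan. The markup is 57 × 1.10 = 62.7, so 63, which also matches. Power is 80.2% at 57 and 84.0% at 63.

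**PONV and respiratory, at the stated 63.** Pooled z-test, with p̄ the mean of the two rates:

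power = Φ{ [ |p1 − p2| − 1.96·√(2p̄(1 − p̄)/n) ] / √(p1(1 − p1)/n + p2(1 − p2)/n) }

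- PONV: p̄ = 0.175; (0.19 − 1.96 × 0.0677)/0.0656 ≈ 0.874; Φ = 80.90%. Stated 80.9%.
- Respiratory: p̄ = 0.216; (0.216 − 1.96 × 0.0733)/0.0708 ≈ 1.022; Φ = 84.66%. Stated 84.7%.

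Both stated powers are correct for the sample size named in their sentence.

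**If patients were lost.** A full 10% loss leaves 63 × 0.9 = 56.7, about 57. The exact column enumerates the binomial outcomes for the same pooled test.

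| n per group | PONV, plan's formula | PONV, exact | Respiratory, plan's formula |
|---|---|---|---|
| 63 | 80.9% | 82.1% | 84.7% |
| 61 | 79.6% | 80.9% | 83.5% |
| 58 | 77.5% | 79.99% | 81.5% |
| 57 | 76.8% | 79.2% | 80.9% |

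By the formula, PONV falls below 80% once two patients per group are lost. In exact terms it stays above 80% down to 59 per group (80.8%) and misses by less than a point at 57. The early crossing comes from the normal approximation. Respiratory power stays above 80% throughout.

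**Scale against the inputs.** At 63 per group, changing the neostigmine PONV rate from 27% to 26% gives 77.4%, and changing the sugammadex rate from 8% to 9% gives 75.5%. One percentage point in a rate taken from a single published study moves power by 3.5 to 5.4 points. Using the whole markup moves it by 80.9 − 76.8 = 4.1 points.

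**Is there a contradiction in the text?** The primary statement solves for n at a fixed power. The other statement gives power at the enrolment so obtained. These are different calculations, each labelled with its own n, and sections 2.3 and 2.7 agree on 63.

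**The case for a change.** The best argument for the concern does not depend on what the markup is for. At any common sample size PONV has about three points less power than the primary: 76.8% against 80.2% at 57, and 80.9% against 84.0% at 63. The section never puts the endpoints on one basis, and two sentences would do it.

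The arithmetic in that argument stands. It also stands that the purpose of the markup is not stated, so a reader cannot tell whether 63 or something nearer 57 is expected in the analysis. But the plan makes no claim that the endpoints are equally powered, and it sets 80% as a target only for the primary. A secondary endpoint that did not determine the sample size breaches nothing at 77%.

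The loss scenario is also weakly supported. PONV is a yes/no question asked every 15 minutes in the PACU until readiness for discharge, and any yes counts (Variables/Time Points of Interest), so there is no later visit to miss. Exclusion after randomisation remains possible, but the documents give no rate for it, and 63 is a minimum. Declaring the markup to be an attrition allowance would put into the plan a fact that only the investigator can supply.

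**Conclusion.** The concern does not hold. The powers of 80.9% and 84.7% are right for 63 per group, the number the plan states and intends to enrol as a minimum. Reporting secondary and exploratory power at planned enrolment is a legitimate choice of presentation.

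A lower figure needs the added assumption that the whole 10% is lost. PONV power is then 76.8% by the plan's formula or 79.2% exactly, and respiratory power is 80.9% by the formula. The primary is unaffected, and no test, sample size or conclusion would change. All these figures rest on two-sided alpha 0.05, which the plan does not state but which reproduces its three figures, and on the borrowed event rates. The unstated purpose of the markup is a missing detail, not a flaw in the power statement.
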